## MEDICAL PROTOCOL (HRP-590)

PROTOCOL TITLE: Brivaracetam to Reduce Neuropathic Pain in Chronic SCI: A Pilot Clinical Trial  
VERSION DATE: 03/18/2024

participation in the study. The medical monitor will also indicate whether he concurs with the details of the report provided by the study investigator. Reports for events determined by either the investigator or medical monitor to be possibly or definitely related to participation, and reports of events resulting in death will be promptly forwarded to the IRB and FDA.

Reporting Adverse Events. Anticipated adverse events (detailed above in 13.0, Risks to Participants) will be identified while interviewing participants, during physical exams, and while reviewing laboratory results. Participants also will be directed to call study staff to report adverse events that may occur between these visits. All adverse events will be noted on the Adverse Events log form that will be kept in the participant's file. Unanticipated adverse events and unanticipated serious adverse events (as defined in CFR Title 21), also will be identified during testing time points and through participant self-reporting between these visits. They will be noted on the Adverse Events Log and promptly brought to the attention of the study PI.

Unanticipated serious adverse events will be reported within 5 working days to the UMN IRB as required.

Follow-up of Adverse Events. In the unlikely event that a participant is injured as a result of this research study, medical care, including emergency treatment will be provided.

Assessment of Risk. This is a moderate risk pilot clinical study. As such, our safety monitoring plan will include a medical monitor: [name]. [name] will review all reported adverse events on a monthly basis with [name], the medical monitor. Additionally, [name] will inform [name] immediately of all study-related unanticipated problems involving risk to volunteers or others, serious adverse events, and all volunteer deaths associated with the protocol, and provide an unbiased written report of the event to the IRB. The medical monitor will comment on the outcomes of the event or problem, and in the case of a serious adverse event or death, comment on the relationship to participation in the study. The medical monitor will also indicate whether he concurs with the details of the report provided by the study investigator. Reports for events determined by either the investigator or medical monitor to be possibly or definitely related to participation, and reports of events resulting in death will be promptly forwarded to the IRB.

## 19.0 Provisions to Protect the Privacy Interests of Participants

### 19.1 Protecting Privacy:

## MEDICAL PROTOCOL (HRP-590)

PROTOCOL TITLE: Brivaracetam to Reduce Neuropathic Pain in Chronic SCI: A Pilot Clinical Trial  
VERSION DATE: 03/18/2024

Study staff will receive HIPAA and data security training to maintain participant confidentiality prior to the initiation of participant recruitment. Non-identifiable research related data will be directly entered by participants into REDCap. REDCap is a secure, web-based application designed to support data capture for research studies. Trained staff will double enter data from de-identified case report forms containing variables collected on questionnaires. All paper form files with personal identifiable information will be stored in locked filing cabinets. Electronic files containing personal identifiers will be stored on Box Secure Storage and REDCap. In the instance that participants engage in a study-related videoconference through the Zoom video-conferencing platform, Zoom does not have access to identifiable protected health information, and they protect and encrypt all audio, video, and screen-sharing data. Zoom sessions will not be recorded or maintained. All study staff will receive training on privacy standards for maintaining participant confidentiality. The informed consent form and the HIPAA form will be signed with eSignature using a REDCap form that is compliant with FDA Title 21 CFR Part 11. For more information on REDCap compliance, please visit: [https://redcap.ahc.umn.edu/surveys/?s=3PT9FY73NC&topics\\_\\_ec=1#ec](https://redcap.ahc.umn.edu/surveys/?s=3PT9FY73NC&topics__ec=1#ec)

Procedures are in place for maintaining the full confidentiality of all information collected. Participant confidentiality will be protected by securing all hard copy study files in locked filing cabinets. Electronic files containing personal identifiers will be stored on Box Secure Storage or REDCap. All study staff receive training on privacy standards for maintaining participant confidentiality. All published reports will be of summary nature and no individual participants will be identified beyond the investigative staff involved in the project.

### 19.2 Access to Participants:

Participants have been fully informed of the ways in which their data will/may be used during the informed consent process. The research team has been trained in conducting these conversations and the participants are also assessed for their understanding of consent prior to signing the consent form or initiating any study procedures.

## 20.0 Compensation for Research-Related Injury

### 20.1 Compensation for Research-Related Injury:

In the unlikely event that a participant is injured as a result of this research study, medical care, including emergency treatment will be provided. The participant's insurance company may be billed for treatment.

MEDICAL PROTOCOL (HRP-590)

PROTOCOL TITLE: Brivaracetam to Reduce Neuropathic Pain in Chronic SCI: A Pilot Clinical Trial  
VERSION DATE: 03/18/2024

20.2 Contract Language: N/A

## 21.0 Consent Process

21.1 Consent Process (when consent will be obtained):

Informed consent will be obtained electronically via REDCap or in person at the CRU (or a location convenient to the participant) by study staff. For participants who meet the inclusion criteria, a qualified member of the study team will follow the informed consent process over Zoom, and the participant will provide consent through the REDCap eConsent form. Prior to obtaining consent, all participants will be given ample time to read the consent form and encouraged to ask questions. Potential participants will be reminded that participation is strictly voluntary and will not affect their current or future care at the UMN or any affiliated institute. Each participant will be told that they will be free to discontinue participation in the experiment at any time, but that discontinuation of the drug must be done under medical supervision to ensure it is done safely. A copy of the signed informed consent form will be sent or given to the participant. Participants will be provided with [name] contact information if questions should arise during the course of the trial. Consent will be obtained only from the participant and we will not seek consent from legally authorized representatives. We will not enroll any participants unable to give consent due to altered mental capacity. We will not enroll children therefore will not obtain assent.

21.2 Waiver or Alteration of Consent Process (when consent will not be obtained): N/A

21.3 Waiver of Written/Signed Documentation of Consent (when written/signed consent will not be obtained): N/A

21.4 Non-English speaking Participants: We will include enrollment of English and Spanish speaking participants. We will provide a translator to interpret consent forms. The interpreters are trained and required to protect participant privacy. Additionally, Co-I [name] will also be available as needed to carry out study procedures in Spanish, correspond with Spanish-speaking participants, and provide Spanish-English translation.

21.5 Participants Who Are Not Yet Adults (infants, children, teenagers under 18 years of age): N/A

## MEDICAL PROTOCOL (HRP-590)

PROTOCOL TITLE: Brivaracetam to Reduce Neuropathic Pain in Chronic SCI: A Pilot Clinical Trial  
VERSION DATE: 03/18/2024

**21.6** Cognitively Impaired Adults, or adults with fluctuating or diminished capacity to consent: N/A

**21.7** Adults Unable to Consent: N/A

- Permission: N/A
- Assent: N/A
- Dissent: N/A

## **23.0 Multi-Site Research**

**23.1** Study-Wide Number of Participants:

20 enrolled participants. 30 screened participants.

**23.2** Study-Wide Recruitment Methods:

We anticipate screening 30 individuals with SCI to recruit and enroll 20 participants across the 2 enrollment sites (Swedish Medical Center/Craig Hospital and University of Minnesota). The PI (Swedish Medical Center/Craig Hospital site) sees over 50 patients a year with severe sublesional neuropathic pain. Therefore, at Swedish Medical Center/Craig Hospital we will recruit potential participants from his clinical practice. The Department of Rehabilitation Medicine houses an ACGME-accredited, 12-month SCI Medicine Fellowship program. This fellowship leverages collaborative relationships with all specialty hospitals in the greater Minneapolis area providing acute inpatient rehabilitation for spinal cord injury, including Fairview Acute Inpatient Center, Minneapolis VA Medical Center, Regions Hospital, and Courage Kenny Rehabilitation Institute. Therefore, we will recruit participants at the University of Minnesota from each of our SCI Medicine Fellowship clinical sites. We will also utilize local patient representative organizations by sharing posters and sample text for social media recruitment. The Rocky Mountain Regional Spinal Injury System at Craig Hospital provides comprehensive inpatient rehabilitation to over 200 newly injured individuals with SCI every year and continues to treat nearly 1,100 individuals with SCI annually in outpatient programs,

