## 5.0 Procedures Involved

### 5.1 Study Design:

This is a multi-center randomized, double-blinded placebo-controlled pilot clinical trial. Each site (Swedish Medical Center/Craig Hospital, UMN) will enroll and study 20 adults, 18 years of age and older with SCI. [name] will serve as PI, and [name] will serve as Co-I at UMN (local site). MRI data analysis will be conducted by [name] (Harvard University). [name] will receive a deidentified dataset and will have no human subject interactions. Research activities at the Swedish Medical Center/Craig Hospital will be conducted under a separate IRB protocol at Craig Hospital.

Participants who meet the eligibility criteria will be randomly assigned to active drug (escalating brivaracetam dose to 100 mg twice daily for 3 months) or placebo based on a randomization schedule developed by our biostatistician. This is a simple computer generated 1:1 scheme that randomly assigns participants to arm A or arm B. Study participants, research coordinators, and study personnel involved in outcomes assessments and analyses will all be blinded. The drug will be provided by RxArtisans pharmacy in Wayzata, MN. The active and placebo capsules will have identical appearance and consistency. Treatment assignment will be known only to the investigational drug pharmacies (RxArtisans). We have registered this pilot study with National Institutes of Health (NIH) clinical trials registry, [www.clinicaltrials.gov](http://www.clinicaltrials.gov) (NCT04379011). The pilot data generated by this effort will be used to power a subsequent multi-center clinical trial.

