### 5.3 Study Duration:

This is a 2-year study. Eligible participants will be enrolled throughout the duration of the study. It is anticipated that study enrollment goal will be met six months prior to study ending in year 2. Individual participant's participation will approximately be three months from time of enrollment into the study. We anticipate the completion of all study procedures, including data analysis and results to report, will take approximately a year once the study has completed all data collection from study participants.

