### **10.0 Local Number of Participants**

#### **10.1 Local Number of Participants to be Consented:**

30 participants are expected to be screened. 20 participants will be enrolled at UMN.

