### **11.0 Local Recruitment Methods**

#### **11.1 Recruitment Process:**

We anticipate screening 30 individuals with SCI to recruit and enroll 20 participants. The UMN healthcare system treats hundreds of patients with SCI each year. Given the large pool available for recruitment, we anticipate no difficulty in recruiting sufficient numbers of persons with SCI who meet the inclusion/exclusion criteria. Recruitment material will accurately reflect the study and will not be coercive.

*For self-referrals from recruitment materials:*

Participants may self-refer if they become aware of the study through recruitment materials, clinicaltrials.gov (or similar websites), or word of mouth referrals. A study-specific webpage will be published ([www.z.umn.edu/SCIPain](http://www.z.umn.edu/SCIPain)). A link to a RedCAP online survey will be shared for individuals to indicate their interest and preferred contact method. Participants will self-enter their contact information prior to consent for contact purposes only.

Potential participants will be identified by the Co-Principal Investigators from among patients under their care and their colleagues. Potential participants will be asked about their interest in the study at the time of a routine care visit. The patient will be given the choice, if interested, to be approached by the investigator in person, over phone or e-mail or have them reach out to the investigator. A flier or recruitment card about the study may be sent to potential participants, asking them to contact the study coordinator if they are interested.

Individuals who respond to the recruitment materials will be taken through a phone screening questionnaire with the study coordinator. If following the phone screen, the potential participant is eligible and interested; the study coordinator will schedule the screening study visit.

*Regional Healthcare Institutions:*

Contacts at regional healthcare institutions that have partnered with the University of Minnesota in previous SCI research will be made aware of this research, including the VA. Flyers and/or postcards/recruitment cards will

MEDICAL PROTOCOL (HRP-590)

PROTOCOL TITLE: Brivaracetam to Reduce Neuropathic Pain in Chronic SCI: A Pilot Clinical Trial  
VERSION DATE: 03/18/2024

be posted around campus, at the VA, on the UMN website (e.g. Brain Body Mind Lab website) and on social media with information about this study.

*Patient Representative Organizations (PRO):*

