### 15.2 Power Analysis:

Part of the goal of this pilot study is to obtain information that can be used for formal sample size estimation, including effect sizes and standard error estimates; therefore, analyses are included here that may not be included in a non-pilot follow-up (including the randomization analyses described below); further, some of the analyses here are exploratory to help in the design of a follow-up study. Also, (1) robust standard errors will be used in all cases to help guard against the effects of heteroskedasticity; (2) although there are a number of outcomes and, therefore, analyses, no adjustments for multiple comparisons will be made in this pilot study as the prime aim is not the level of statistical significance but rather the estimation of results needed for planning a follow-up. Of course, when disseminating our findings we will report the number of tests performed and the actual p-values so that readers can make their own adjustments if wanted.

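### Planned enrolment is contradictory: 40 in total by Section 5.1 (20 at each of two sites), but 20 across both sites by Sections 23.1 and 23.2

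*Combined protocol and SAP*

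**What the plan says.** Five sections of the current protocol (version dated 03/18/2024) bear on the planned number.

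- Section 5.1 (Study Design): "Each site (Swedish Medical Center/Craig Hospital, UMN) will enroll and study 20 adults".
- Section 10.1 (local number to be consented): "30 participants are expected to be screened. 20 participants will be enrolled at UMN".
- Section 11.1 (local recruitment process): "We anticipate screening 30 individuals with SCI to recruit and enroll 20 participants. The UMN healthcare system treats hundreds of patients".
- Section 23.1 (study-wide number of participants): "20 enrolled participants. 30 screened participants".
- Section 23.2 (study-wide recruitment): the plan is to "enroll 20 participants across the 2 enrollment sites", with both sites named and 30 again given as the number screened.

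Two other sections depend on this number without stating it. Section 5.3 says "It is anticipated that study enrollment goal will be met six months prior to study ending in year 2". Section 15.2, headed Power Analysis, gives no sample size and says instead: "Part of the goal of this pilot study is to obtain information that can be used for formal sample size estimation".

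**The concern.** The same pair of figures, 20 enrolled from 30 screened, appears once as UMN's own target and once as the target for both sites together. Both cannot be true if the second site recruits anyone, and Section 5.1 gives that site 20 of its own.

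Planned sample size is a basic design quantity. Here it determines how precisely the pilot estimates the quantities it is meant to hand on to the next trial, and how much the safety endpoint can say about adverse events. It is also the yardstick for recruitment. With two values for the enrolment goal, a reader who later sees about 20 participants cannot tell whether the trial met its target or reached half of it, and cannot judge a shortfall at either site.

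**Working it through.** **Inputs**

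| Section | Scope | Enrolled | Screened |
|---|---|---|---|
| 5.1 | each of two sites | 20 per site | not given |
| 10.1 | UMN | 20 | 30 |
| 11.1 | local (UMN) | 20 | 30 |
| 23.1 | study-wide | 20 | 30 |
| 23.2 | both sites together | 20 | 30 |

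**Step 1: can the study-wide 20 be reproduced from the site figures?** 2 sites × 20 = 40, not 20. The ratio is 40/20 = 2.

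**Step 2: what is left for the second site?**
- If the total is 20 and UMN enrols 20: 20 − 20 = 0, although Section 5.1 gives that site 20 and Section 23.2 describes recruiting there.
- If the total is 40: 40 − 20 = 20, which agrees with Section 5.1 and contradicts Sections 23.1 and 23.2.

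**Step 3: do the screening numbers fit?** A total of 40 cannot come from 30 screened, since 40 exceeds 30. At the stated UMN yield of 20 from 30, enrolling 40 needs 40 ÷ (20/30) = 60 screened. That assumes the same yield at the other site, for which the documents give no figure.

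**Step 4: does the statistical section settle it?** No. Section 15.2 gives no sample size, power, effect size, standard deviation (SD) or dropout rate, so there is no sample-size calculation to reproduce.

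**Step 5: what does the factor of 2 mean for precision?** This is an illustration only. It assumes equal arms (the simple 1:1 scheme does not guarantee them), no dropout, and an equal-variance comparison of two means. With n per arm and df = 2n − 2:

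- 95% confidence interval half-width for a mean difference, in SD units: t(0.975, df) × √(2/n).
- Upper limit of the two-sided 95% interval for the SD, as a multiple of the estimate: √(df / χ²(0.025, df)).
- One-sided 95% upper limit for an event rate after zero events on active drug: 1 − 0.05^(1/n).

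| | N = 20 (n = 10) | N = 40 (n = 20) |
|---|---|---|
| Half-width, mean difference | 0.94 SD | 0.64 SD |
| Upper limit for the SD | 1.48 × estimate | 1.29 × estimate |
| Upper limit after zero events | 26% | 14% |

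With an assumed 20% dropout (n = 8 and n = 16) the pairs become 1.07 and 0.72 SD, 1.58 and 1.34 times the estimate, and 31% and 17%.

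**The case against.** The contradiction itself is hard to dispute; the case on the other side is about how much it matters.

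- **Enrolment is finished.** The revision-history entry for this version notes that enrolment is complete. The planned number can no longer steer recruitment, and the pilot's precision now depends on the numbers actually enrolled and analysed. This stands, and it lowers the urgency. It does not remove the need for a recorded target against which actual enrolment can be reported.
- **No analysis uses the number.** No power is claimed and no decision rule depends on the sample size; Section 15.2 leaves formal sizing to the follow-up study. This also stands. The error is in the stated design, not in an analysis.
- **The evidence leans one way.** Sections 5.1, 10.1 and 11.1 fit together at 40. Section 23 alone disagrees, and it repeats the local pair of figures exactly. Version 4.0 clarified that the trial is multi-centre, so local figures may simply have been carried into Section 23. This is plausible but not shown.
- **The second site has its own protocol.** Section 5.1 says that site works under a separate ethics protocol. That explains why Section 10 is local only. It does not explain Section 23, which is headed as study-wide and names both sites.
- **The precision figures are generic.** The plan uses linear regression with group, time and interaction terms and robust standard errors, not the simple comparison above. This is fair: the figures show only the order of the difference, and the finding does not rest on them.

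**Conclusion.** The concern holds. The current text gives a planned total of 40 in one place and 20 in another, and no reading reconciles them. The total of 40 is not printed, but it follows directly from 20 at each of two named sites. All the figures come from the body of the current version, not from superseded text.

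The discrepancy is a factor of 2 in planned enrolment, together with a study-wide screening figure of 30 that is too small for a total of 40. This conclusion needs no statistical assumption. The precision illustration does: under the stated simplifications, the half-width for a mean difference is 0.94 SD for a total of 20 and 0.64 SD for 40. Which total was intended cannot be settled from the documents.

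**What to change.** State one planned study-wide number enrolled and one study-wide number screened, each with its split by site, and make Sections 5.1, 10.1, 11.1, 23.1 and 23.2 agree with them. The sponsor must supply the intended total.

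The cost is wording only, with no change to design or analysis. All five sections need checking, but not all need new numbers. If the total is 40 with 20 per site, Sections 23.1 and 23.2 change. If it is 20, Section 5.1 changes, and so do Sections 10.1 and 11.1 unless UMN was to enrol everyone.

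Because enrolment has closed, the correction should identify the figure as the original target, so that actual enrolment at each site can be reported against it. Adding the precision that the reconciled number gives would be useful but is optional.

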## MEDICAL PROTOCOL (HRP-590)

PROTOCOL TITLE: Brivaracetam to Reduce Neuropathic Pain in Chronic SCI: A Pilot Clinical Trial  
VERSION DATE: 03/18/2024

including [name] neuropathic pain clinic. Similarly, the University of Minneapolis SCI system of care treats over 200 newly injured individuals with SCI every year. Given the large pool available for recruitment, we anticipate no difficulty in recruiting sufficient numbers of persons with SCI who meet the inclusion/exclusion criteria.

**23.3 Study-Wide Recruitment Materials:**  
We will use flyers to recruit participants.

**23.4 Communication Among Sites:**  
The site PIs ([name], [name]) will communicate in person daily with their local teams to discuss experimental design, data analysis, and all administrative responsibilities. The research team (all key personnel across the 2 sites) will meet virtually on a weekly basis to monitor project progress and to trouble-shoot.

